8.12. Other Safety Assessments

8.12.1. Columbia-Suicide Severity Rating Scale (C-SSRS) - Assessment of Suicidality

The C-SSRS will be used to assess the patient's suicidal ideation (severity and intensity) and behavior (Posner et al 2011). The C-SSRS is a semi-structured interview that captures the

occurrence, severity, and frequency of suicide-related thoughts and behaviors. Any positive answer to the behavior sub-components at screening or baseline identifies a patient with "Suicidal Behavior at Screening" or "Suicidal Behavior at Baseline" respectively. The C-SSRS interview will be administered at screening (baseline/screening version), and the "Since Last Visit" version will be administered at all other time points, as described in Table 1 and Table 2 of the study protocol).

For post-screening/post-baseline visits, any positive answer to the behavior subcomponents in any of the post screening or baseline assessments, identifies a patient as with "Suicidal Behavior Post Dosing". Same derivation will be done also for "Suicidal Ideation post Dosing". A patient identified with either "Suicidal Behavior Post Dosing" or with "Suicidal Ideation Post Dosing" is also classified as with "Suicidal Behavior or Ideation Post Dosing", the derivation should be done separately for period 1 and for the integrated study periods.

Frequency counts and percentages of the C-SSRS outcomes: Suicidal Behavior at Baseline in Period 1 and integrated periods, Suicidal Ideation at Baseline in Period 1 and integrated periods, Suicidal Behavior or Ideation at Baseline in Period 1 and integrated periods, Suicidal Behavior Post Dosing, Suicidal Ideation Post Dosing, Suicidal Behavior or Ideation Post Dosing, and shifts from baseline for Period 1 and integrated periods will be summarized.

8.12.2. Abnormal Involuntary Movement Scale (AIMS)

The AIMS will be performed at the time points specified in Table 1 and Table 2 of the study protocol. The AIMS scores the occurrence of tardive dyskinesia in patients receiving neuroleptic medications. The AIMS is a 14-item scale that includes assessments of orofacial movements, extremity and truncal dyskinesia, examiner's judgment of global severity, subjective measures of awareness of movements and distress, and a yes/no assessment of problems concerning teeth and/or dentures. Higher scores indicate greater severity of the condition.

AIMS total score will be calculated as a sum of items 1 through 7.

The AIMS total score and the individual score for each of the AIMS items 8-10 and changes from baseline will be presented, separately for Period 1 and for the integrated study periods, using descriptive statistics. Shift from baseline analysis of AIMS items 11-14 during Period 1 and during integrated study period will be presented.

Safety analysis set will be used as appropriate.

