4. GENERAL ISSUES FOR DATA ANALYSIS

4.1. General

Descriptive statistics for continuous variables include n, mean, standard deviation (SD), median, minimum, and maximum. When appropriate, least squares means and standard errors (SE) are presented. Descriptive statistics for categorical variables include patient counts and percentages. Missing categories will be displayed as appropriate.

For the CSR and IDMC closed reports, summary tables by treatment groups will have 2 versions – (a) summary tables for Period 1; (b) summary tables for the integrated periods including patients from both Periods (Period 1 & Period 2), unless otherwise specified. For IDMC open reports, a summary tables for Period 1 and Period 2 will be generated and will only be presented overall (total).

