4.4. Study Days and Visits

Study days will be numbered relative to the first day of IMP administration (i.e., the first administration in Period 1). The start of treatment (Day 1) is defined as the date for which a patient receives the first dose of study drug, as recorded on the Case Report Form (CRF). Days will be numbered relative to treatment start (i.e., ..., -2, -1, 1, 2, ...; with Day 1 being the first day of study drug administration and day -1 being the day before the first day of study drug administration).

In case the Early Termination (ET)/End-of-Treatment (EOT) visit occurred on the allowed time window for any scheduled visit (according to Table 1 and Table 2 of the study protocol), and the scheduled visit results are missing, the results from the overlapping ET/EOT visit will be mapped to the scheduled visit.

In case the EOT or Follow-up visit assessments were collected out of the allowed time window, assessment results will be excluded from the by-visit summary tables but will be included in relevant listings. In addition, if there are multiple assessments at a post-baseline visit day, then the last non-missing assessment at that visit will be used, unless otherwise specified.

For the by-visit summary tables, only scheduled visits, EOT and follow-up visits will be presented. The ET visit will not be presented, and unscheduled visits will not be mapped or presented. For the 'at any time' summary statistics in the shift tables and in the presentation of Potentially Clinically Significant (PCS) summaries, all visits will be used (including unscheduled visits).

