8.12.3. Simpson-Angus Scale (SAS)

The SAS will be performed at the time points specified in Table 1 and Table 2 of the study protocol. The SAS is a 10-item instrument for the assessment of neuroleptic-induced Parkinsonism. The items on the scale include measurements of hypokinesia, rigidity, glabellar reflex, tremor, and salivation. Each item is rated on a 5-point scale (0 to 4), with a higher score indicating greater severity of symptoms. The mean score is calculated by adding the individual item scores and dividing by 10.

The SAS mean score and changes from baseline during Period 1 separately and during the integrated study periods will be presented using descriptive statistics by treatment group using safety analysis set.

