8.12.4. Barnes Akathisia Rating Scale (BARS)

The BARS will be performed at the time points specified in Table 1 and Table 2 of the study protocol. The BARS is an instrument that assesses the severity of drug-induced akathisia. The BARS includes 3 items for rating objective restless movements, subjective restlessness, and any subjective distress associated with akathisia that are scored on a 4-point scale of 0 to 3, and summed yielding a total score ranging from 0 to 9. The BARS also includes a global clinical assessment of severity scored on a scale of 0 to 5. Higher scores are indicative of greater severity of akathisia.

BARS total score, global clinical assessment of severity values, and changes from baseline to each visit will be summarized using descriptive statistics - during Period 1 and integrated study periods by treatment group.

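### The SAP counts no patients as worsened on AIMS items 1-10, SAS or BARS and gives a shift table only to AIMS items 11-14, the dental questions by the order of the description

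*SAP*

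**What the plan says.** AIMS, SAS and BARS are named secondary safety endpoints (SAP 1.1). The SAP handles them as follows.

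- AIMS (SAP 8.12.2): "AIMS total score will be calculated as a sum of items 1 through 7". Then "The AIMS total score and the individual score for each of the AIMS items 8-10 and changes from baseline will be presented", using descriptive statistics. The only shift analysis is the last sentence on the scale: "Shift from baseline analysis of AIMS items 11-14 during Period 1 and during integrated study period will be presented".
- SAS (SAP 8.12.3): "The SAS mean score and changes from baseline during Period 1 separately and during the integrated study periods will be presented using descriptive statistics".
- BARS (SAP 8.12.4): "BARS total score, global clinical assessment of severity values, and changes from baseline to each visit will be summarized using descriptive statistics". This covers the 0-9 total and the 0-5 global rating.
- Descriptive statistics are defined in SAP 4.1: "Descriptive statistics for continuous variables include n, mean, standard deviation (SD), median, minimum, and maximum".
- By-visit tables (SAP 4.4): "The ET visit will not be presented, and unscheduled visits will not be mapped or presented". The same section maps an ET result to a scheduled visit when it falls in that visit's window and the scheduled result is missing. It also displays EOT and FU visits. It uses all visits, including unscheduled ones, only for at-any-time rows of shift tables and for summaries of potentially clinically significant values.

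**The concern.** The question for an antipsychotic safety table is how many patients, by dose, developed akathisia, parkinsonism or dyskinesia that they did not have at baseline. No planned table on these scores answers it. There is no shift table, no worst post-baseline value and no count of patients who worsened.

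Patients taper prior oral antipsychotics before randomization (Protocol 4.1). Residual symptoms may therefore fade in some patients while new ones appear in others, and a mean change nets the two. Patients who stop early may be those with the worst ratings. Their ET rating is collected, but it reaches the by-visit tables only by the mapping rule.

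**Working it through.** The plan states no figure on this point to reproduce. The check compares sections, then does two small calculations.

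**1. Which AIMS items are 11-14.** The SAP does not number the content. It describes movement items, then global severity, then awareness and distress, and finally "a yes/no assessment of problems concerning teeth and/or dentures". Items 1-7 form the total and items 8-10 are shown singly, so 11-14 should be the dental block and item 8 global severity. This is an inference from the order.

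**2. What other safety data get.** Laboratory tests have shifts with an any-visit row and incidence of significant values (SAP 8.6). Weight has percentage bands (8.7). ECG uses the worst post-baseline finding (8.9). The Columbia suicidality scale has an any-time-post-dosing rule with shifts (8.12.1). Of the extrapyramidal scores, only AIMS items 11-14 have a table type to which the all-visits rule in SAP 4.4 could apply.

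**3. What the planned statistics show (illustrative values).** Planned arm size is 640/4 = 160. Assume 10% (16 patients) go from BARS global 0 to 3, and 15% (24 patients) go from 2 to 0.

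- Mean change = (16 × 3 − 24 × 2)/160 = 0.00.
- SD of change = √[(16 × 9 + 24 × 4)/160] = √1.5 = 1.22; minimum −2, maximum +3.
- A placebo arm with the same 24 resolving and no new cases: −(24 × 2)/160 = −0.30.

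The spread and the Period 1 placebo difference of 0.30 show that something happened. Neither shows that 16 patients worsened.

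If nobody improves and 5% to 10% (8 to 16 patients) worsen, the mean moves little:

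- BARS global, +2 each: 8 × 2/160 = 0.10 to 16 × 2/160 = 0.20.
- SAS mean score, +6 item points each (0.6 on the mean): 0.03 to 0.06.
- AIMS total, +4 each: 0.2 to 0.4.

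**4. When an ET rating can be mapped.** Nominal days are used, with windows from Protocol 4.1 and the scale schedule from Protocol Appendix B.

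- Period 1, days 2-56 (55 days). The scales are rated at days 8, 15, 22, 36, 43 and 50 (±2 days) and at days 29 and 57 (±3 days). Days covered: 6 × 5 + 7 + 3 = 40, and 40/55 = 73%. The gaps are days 2-5, 11-12, 18-19, 25, 33, 39-40, 46-47 and 53.
- Period 2, days 61-392 (332 days). The scales are rated at weeks 20, 32 and 44 (±3 days). Days covered: 3 × 7 = 21, and 21/332 = 6%.
- If every monthly in-clinic visit counted, whether or not it carries the scales: 11 × 7 = 77, and 77/332 = 23%. The SAP does not say whether weekly telephone visits count as scheduled visits for mapping.

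These are shares of days, not of patients. ET dates need not be evenly spread, and real visit dates run from the previous injection.

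**The case against.** A reader might draw four stronger conclusions, none of which the documents support.

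- **That ET ratings are left out altogether.** SAP 4.4 maps those in an empty scheduled window. Patients who stop are also encouraged to attend EOT and FU, where all three scales are rated and the visits displayed. An ET visit inside the EOT window may be combined with it (Protocol 4.1). The loss falls mainly on Period 2 patients who miss EOT and FU or attend out of window.
- **That only means are shown.** SD, median, minimum and maximum are planned. The SAP does not rule out category counts for the 0-5 BARS rating, although counts at one visit would still not be crossed with baseline.
- **That new symptoms can average out unseen.** In Period 1 the placebo arm should share any fading of residual symptoms, so an excess on active treatment would appear as a difference between arms. This does not help the integrated tables, which exclude placebo data from Period 1 (SAP 8.1).
- **That extrapyramidal harm is hidden, or known only from spontaneous complaints.** Patients are questioned at each contact, and observed signs are recorded (Protocol 8.1.2). Abbreviated examinations check muscle tone, gait and involuntary movements (Protocol 8.5). Treatment-emergent events are tabulated by arm through the ET visit, with separate summaries of events causing withdrawal (SAP 8.4). Concomitant medications, which include the permitted anti-parkinsonian and akathisia drugs, are summarized (SAP 8.10). The list of adverse events of special interest is blacked out, so nothing can be inferred from it.

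It can also be said that shift tables for yes/no items and change scores for graded items simply follow data type. That is fair as an explanation. However, the SAP already uses worst-value and any-time rules for other safety data, and adverse-event counts do not report rated change from baseline.

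**Conclusion.** The point stands as a minor reporting gap. No patient-level worsening analysis is planned for AIMS items 1-10, SAS or BARS, while AIMS items 11-14 get a shift table. By-visit statistics can show that someone worsened, but not how many. The gap is greatest in the integrated tables, where the Period 1 placebo comparison is absent and only about 6% of Period 2 days allow an ET rating to be mapped to a visit carrying these scales. It is smaller in Period 1, where the figure is about 73% and a concurrent control exists.

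The conclusion rests on reading items 11-14 as the dental block, on nominal visit days, and on the SAP text as published. The percentages in the averaging example are assumed and serve only as illustration. The primary analysis is not affected.

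**What to change.** In SAP 8.12.2 and 8.12.4, add by-arm shift tables of baseline against worst post-baseline value for AIMS item 8 and the BARS global rating (0-5). Produce them for Period 1 and for the integrated periods, and state that all visits count, including ET and unscheduled ratings. The scales are not on the standard unscheduled-visit list, so those ratings exist only where the investigator added them.

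Optionally, in 8.12.2-8.12.4, add the number and percentage of patients whose AIMS items 1-7 total, SAS mean score or BARS total worsened from baseline by a margin set before unblinding. A margin is preferable to counting any increase, because a one-point rise at any of eight weekly ratings would pick up rating noise. AIMS items 11-14 may stay as planned.

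The cost is SAP wording and a few tables from data already collected. Worst-value summaries will catch some rating noise, so the Period 1 tables should be read against placebo. If Period 1 has already been unblinded, SAP 2.6.2 requires the addition to be disclosed in the study report.

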8.12.3. Simpson-Angus Scale (SAS)

The SAS will be performed at the time points specified in Table 1 and Table 2 of the study protocol. The SAS is a 10-item instrument for the assessment of neuroleptic-induced Parkinsonism. The items on the scale include measurements of hypokinesia, rigidity, glabellar reflex, tremor, and salivation. Each item is rated on a 5-point scale (0 to 4), with a higher score indicating greater severity of symptoms. The mean score is calculated by adding the individual item scores and dividing by 10.

The SAS mean score and changes from baseline during Period 1 separately and during the integrated study periods will be presented using descriptive statistics by treatment group using safety analysis set.

8.12.4. Barnes Akathisia Rating Scale (BARS)

The BARS will be performed at the time points specified in Table 1 and Table 2 of the study protocol. The BARS is an instrument that assesses the severity of drug-induced akathisia. The BARS includes 3 items for rating objective restless movements, subjective restlessness, and any subjective distress associated with akathisia that are scored on a 4-point scale of 0 to 3, and summed yielding a total score ranging from 0 to 9. The BARS also includes a global clinical assessment of severity scored on a scale of 0 to 5. Higher scores are indicative of greater severity of akathisia.

BARS total score, global clinical assessment of severity values, and changes from baseline to each visit will be summarized using descriptive statistics - during Period 1 and integrated study periods by treatment group.

8.12.5. Calgary Depression Scale for Schizophrenia (CDSS)

The CDSS will be performed at the time points specified in Table 1 and Table 2 of the study protocol. The CDSS is specifically designed to assess the level of depression separate from the positive, negative, and extrapyramidal symptoms in schizophrenia. This clinician-administered instrument consists of 9 items, each rated on a 4-point scale from 0 (absent) to 3 (severe) that are added together to form the CDSS depression score for the patient.

[figure not shown]
Descriptive statistics of CDSS depression score values and changes from baseline to each visit will be presented - during Period 1 and integrated study periods by treatment group.

9. LOCAL TOLERABILITY VARIABLES AND ANALYSIS

Term	Percentage (%)
GDP	98
Inflation	98
Interest rates	98
Central bank	98
Monetary policy	98
Quantitative easing	98
Inflation targeting	98
Interest rate hike	98
Interest rate cut	98
Interest rate parity	60
Nominal interest rate	98
Real interest rate	98
Nominal GDP	98
Real GDP	98
Nominal exchange rate	98
Real exchange rate	98
Nominal income	50
Real income	98

Table 4: Assessment of Local Tolerability (Injection Site Findings)

9.1. Assessment of Local Tolerability and Pain

9.2. All-cause Discontinuation Rate Assessment

All-cause discontinuation rates and discontinuation from treatment rates due to adverse events (dropout rates) will be calculated as the number of patients who withdrew early for all reasons, and the number of patients who withdrew early due to adverse events, respectively, divided by number of patients in each treatment group, and will be presented using descriptive statistics.

Time to all-cause discontinuation will be calculated as the discontinuation date minus the randomization date plus 1. The randomization date for the integrated study periods will be defined in accordance with treatment assignment in period 1; for patient who was randomized to placebo in period 1, the randomization day is the day of randomization to period 2, and for patient who was randomized to one of the three active treatment group in period 1, the randomization date is the day of randomization to period 1.

Kaplan-Meier curves for the time to discontinuation as a result of all causes will be plotted by treatment group, for period 1, and for the integrated study period.

The safety analysis set will be used for the analysis.

10. PHARMACOKINETIC ANALYSIS

Topic	Percentage
Global warming	98
Evolution	95
Big Bang theory	92
Quantum mechanics	88
Neuroscience	85
String theory	82
Dark matter	80
Dark energy	78
Black holes	65
The theory of relativity	62

11. PHARMACODYNAMIC ANALYSIS

Pharmacodynamic analysis is not planned this study.

12. PHARMACOKINETIC/PHARMACODYNAMIC ANALYSIS

The pharmacokinetic/pharmacodynamic analysis will be detailed in a separate analysis plan, and results will be reported separately from the main study results.

13. BIOMARKER AND PHARMACOGENETIC ANALYSIS

14.

[REDACTED]

[REDACTED]

[REDACTED]

15. INDEPENDENT DATA MONITORING COMMITTEE - EFFICACY EVALUATION

15.1. General

There is no interim analysis in this study to demonstrate early efficacy or futility. However, a presentation of summary statistics for primary endpoint will be displayed as part of the general risk benefit evaluation that the IDMC might require.

The efficacy analysis set (Section 3.1) will be used for the interim analysis. Summaries will be presented by treatment group as randomized and for overall (total), unless specified otherwise. Only data from Period 1 will be considered for efficacy purposes.

15.2. Conditional Power Evaluation

Due to the ultra-fast recruitment to the study in the first IDMC meeting where the criterion of randomizing at least 50% of patients was met, enrollment was nearly complete. Consequently, conditional power deemed unnecessary.

16. STATISTICAL SOFTWARE

All data listings, summaries, and statistical analyses will be generated using SAS® version 9.4 or later.

17. CHANGES TO ANALYSES SPECIFIED IN THE STUDY PROTOCOL

17.1. Primary Efficacy Estimand

The primary efficacy estimand was modified after protocol approval to allow the use of measurements after a short use of prohibited oral antipsychotic medication during the first 6 weeks in Period 1. This change was based on the understanding of the study team that there are few cases of patients that received prohibited antipsychotic medication early after randomization, and that a short term use of prohibited antipsychotics as part of the management of acute agitation in schizophrenia exacerbation during the first 6 weeks of the study is not expected to affect the treatment effect at week 8 nor the interpretation of the results. Moreover, this approach reflects more accurately the real world management of patients with schizophrenia experiencing an exacerbation and thus would support the principle of intention to treat.

17.2. Conditional Power Evaluation for IDMC

Initially this study's accrual period was expected to be 19 months, however at the time of writing this SAP, the revised expected accrual period is 11 months. As stated in the protocol, a conditional power calculation was planned to be provided to the IDMC when 50% of patients completed Visit 11 as a means of evaluating whether termination of the study was warranted if safety concerns arose. However, since the accrual rate is much higher than anticipated, it is now expected that at the time of reaching 50% accrual, the additional information gained for the remainder of the study would be limited. In fact, at the next planned IDMC meeting, there was only approximately 10% of person-time remaining before the end of accrual in Period 1 (i.e., the time at which efficacy will be evaluated).

Therefore, given these calculations that support an unexpected fast accrual rate, it has been decided that the conditional power analysis will not be conducted as planned. This decision was vetted with the IDMC and the final arbitration will be documented in the IDMC meeting minutes.

17.3. While on Treatment Estimand

This estimand for analyzing efficacy endpoints using the treatment policy strategy replaces the while on treatment estimand.

17.4. Estimand Using the Modified Treatment PolicyStrategy

This estimand is planned to extend the understanding of the treatment effect estimated by the treatment policy strategy for evaluating the 'true' treatment effect of TV-44749 versus placebo on efficacy endpoints, not confounded by concomitant use of other antipsychotics from baseline to week 8.

APPENDIX A. LIST OF DISALLOWED MEDICATIONS

The following list describes the restricted medications for the study due to interactions with cytochrome P450 1A2. Several medications may require dose adjustments or specific monitoring when combined with olanzapine. This should be assessed based on the ZYPREXA official label.

For any questions about prohibited medications, the sponsor or medical monitor should be contacted.

Medication class	Drug name
Antidepressants	Fluvoxamine
Antipsychotics	Any known antipsychotics besides oral olanzapine at screening and TV-44749
Antibiotics	Rifampin
Antiepileptics	Carbamazepine

